ANNEX VIII: MODIC CHANGES
ANNEX IX: RESEARCHER SIGNATURES PAGES A25
ANNEX X: INSURANCE POLICY
ANNEX XI: INSURANCE CERTIFICATE (Art.8; RD223 / 2004) A27

1. SUMMARY

Type of request:

Phase I-II, single-center, prospective, randomized, blinded ** and controlled clinical trial for the treatment of lumbar degenerative disc disease with allogeneic mesenchymal cells (MSV *), with two arms with 12 patients each. In the experimental arm, cells will be administered locally in the nucleus pulposus area of the affected segment "Ex Vivo" expanded allogeneic mesenchymal cells with the IBGM GMP procedure (MSV; PEI No. 10-134; authorized by the AEMPS). The control arm will infiltrate the area of the paravertebral musculature close to the injury with saline solution containing mepivacaine at 1% in the same volume and subject to the same maneuvers as the intervention on the arm experimental.

** Double blind, masked for the patient and evaluators performing the analysis of the results, open to the doctor who applies the cells.

Data relating to the Sponsor:

Citospin, Scientific Park of the University of Valladolid R + D Building, [name] NIF: NIF. B-47673538 Title of the clinical trial: Treatment of lumbar degenerative disc disease with allogeneic mesenchymal cells (MSV *). * MSV = Mesenchymal cells of the bone marrow prepared by the procedure of IBGM of Valladolid.

Protocol Code: Disc_allo_MSV Eudra-CT: 2012-004444-30

Experimental and control drug: dose, pharmaceutical form, route of administration, therapeutic group:

Experimental drug: The investigational drug or product is MSV, which is Mesenchymal bone marrow stromal cells obtained from healthy donors with negative serology (NAT; nucleic acid technology) and processed according to procedure of the IBGM (PEI Num. 10-134; approved by AEMPS), with the following characteristics: \Box Cell dose: 25x10e6 ± 5x10e6 MSV per disk.

□ Presentation: 2 ml of cell suspension in Ringer-lactate isotonic with 0.5% human albumin and 5 mM glucose in a 5 ml syringe. Stability:> 12 hours at 4-20 °C

□ Administration: Injection into the nucleus pulposus area of the affected disc

□ Therapeutic Group: Cell Therapy

Control drug: Injection of 2 ml of 1% mepivacaine in saline serum (see section 2.4). in the paravertebral musculature close to the injury, using the same volume and the same maneuvers as the intervention in the experimental arm.

Cell Production

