In the arm experimental mesenchymal cells obtained from healthy donors purified and expanded under GMP conditions using our protocol, authorized by the AEMPS (MSV, PEI No. 10-134). MSVs will infiltrate the affected intervertebral discs. Whenever possible (because there is sufficient material and explicit consent), use surplus cells from patients undergoing MSV therapy as donors autologous, which would significantly simplify the procedure. In the control arm it will infiltrate the area of the paravertebral musculature near the injury with saline solution containing 1% mepivacaine in the same volume and subject to the same maneuvers as the intervention in the experimental

arm. Study participants will be offered the possibility of receiving MSV treatment once the study is completed if it is demonstrated beneficial and the patient so wishes. The application of the cells will be carried out in the Valladolid University Clinical Hospital. The evaluation of the response to treatment will be blind and will be followed by the evolution of the indices of low back pain, disability and quality of life, as well as the improvement of the dehydration of the treated segments, quantified from magnetic resonance images (T2 sequence).

2.2. EPIDEMIOLOGY OF DEGENERATIVE DISC DISEASE. REPERCUSSION ECONOMIC AND SOCIAL.

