4.2 Overall study design

The study consists of 2 arms, one experimental with allogeneic MSV, and another control in the to be injected into the area of the paravertebral muscles near the injury saline serum containing 1% mepivacaine (1 ml of 2% mepivacaine + 1 ml of saline) in identical volume and subject to the same maneuvers as the intervention on the arm experimental. Participants in the study will be offered the possibility of, once completed the study, receive MSV treatment if it proves beneficial and the patient so wishes. The inclusion criteria in both arms are identical, but after recruiting patients will be randomly assigned to one of the treatments. The Cell manufacturing will be carried out by Citospin at the facilities of the Park Scientist of the UVa and the application and monitoring will be carried out at the Clinical Hospital University of Valladolid. 24 patients diagnosed with low back pain and / or low back pain attributable to disc degeneration and evidence of proven continuity of the external fibrous ring in the magnetic resonance image. The patients will be evaluated clinically, by the previous imaging studies (X-ray and MRI). If they are considered inclusive, they will be provided with the information regarding the clinical trial and the "Patient Information Sheet" (Annex II), citing them for the Inclusion visit. In the "Inclusion Visit", if the patient decides to participate in the trial, they must sign the "Informed Consent Document" and a visit will be scheduled for the practice of MRI and radiographs, which will be considered the pattern on which the possible determinable changes in the controls at 6 and 12 months. If you are MRI and X-rays have been recently performed and their characteristics are valid for the study, its repetition can be avoided. In this visit, basic analytics will also be requested, serology for HIV, lues and hepatitis B and C, and a serum sample will be obtained that will be sent to the Cell Production Unit for filing in the Seroteca. Although the Positive serology is not a criterion for exclusion of the recipient in the present test, it will be performed for epidemiological and preventive purposes. At the next visit (V0), it will be verified that all the inclusion criteria persist and that no exclusion is presented and the patient will be randomized (blind for him) in one of the two treatment groups and the date of implantation of MSV (V1). Once the mobile application is made, the patients will be followed up safety and to determine efficacy as established in the visit program (V2 to V5, see later).

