7.2.1. Visiting Program

Pre-Inclusion: In patients who come for consultation and whose medical history and examinations complementary, including X-rays and / or MRI, presume an orientation diagnosis with the possibility of inclusion in the trial, presenting all the criteria of inclusion and none of exclusion, the treatment regimen will be prescribed according to the standard and then they will be informed of the possibility of inclusion in the EC. They will deliver the "Patient Information Sheet" (Annex II) and, if its decision is affirmative, Inclusion procedures will begin on a future visit.

Visit 0. Inclusion. May comprise more than one physical visit. If the patient confirms that want to join the trial, you will be asked to sign the "Consent Document Informed "(Annex II). You will be ordered new MRI and radiographic scans with the mandatory characteristics of the study unless these examinations had already been performed previously within a period of no more than 6 months. Completed analytics will be requested with the regulated serology for determination of HIV, Hepatitis and Lúes and test of pregnancy if you are a woman of childbearing age. Although positive serology is not a reason for exclusion in this trial, it will be done for epidemiological reasons. After checking the inclusion and exclusion criteria, the clinical history will be made, including data referring to low back pain and discopathy, treatments carried out, analytics and imaging tests to define the characteristics of the same and carry out the measurements that will be taken as a standard of future explorations. Low back pain evaluation questionnaires will be passed (VAS), disability (Oswestry) and quality of life (SF-12). It will be scheduled on the day of the intervention (V1) and the X-ray and MRI tests will be performed, if they had not already been performed.

Visit 1 (day 1). Placebo injection or allogeneic MSV, depending on the clinical trial arm. Visit 2 (8 days): Safety assessment. Includes analytical control.

Visit 3 (3 months): Safety assessment. EVA, Oswestry and SF-12 questionnaires. RX. Visit 4 (6 months): Safety assessment. EVA, Oswestry and SF-12 questionnaires. RX. RM.

Visit 5 (12 months) Safety assessment. EVA, Oswestry and SF-12 questionnaires. RX. RM.

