11.2.1.1 Radiographic criteria

Adams stage 2-4 classification (Adams et al., 1986), with (fibrous ring capable of contain the cell implant), used for inclusion or exclusion purposes in the assay. In profile radiography carried out with the same technical characteristics and times (before noon) the height of the intervertebral space in millimeters will be measured, this being the

variable that will be compared with the measurements that occurred over time (6 and 12 months after MSV implantation). An increase in height will be understood as an indication of rehydration disc associated with an increase in proteoglycans and cellularity of the NP. Descriptive analysis of the observed values will be expressed by the mean, standard derivation, interval of 95% confidence of the mean. To find out if there are differences between baseline and at 6 and 12 months the Wilcoxon nonparametric test for paired data will be used. So Optional, the study will be repeated at 12 months evaluating changes in the leading. The analysis descriptive of the observed values will be expressed by the mean, standard deviation, 95% confidence interval of the mean.

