11.2.1.2 Quantitative MRI criteria

Quantitative density evaluations will be carried out in the "ROIs" (Regions of interest) of the area of the nucleus pulposus of the affected segment and of the 3-5 healthy neighboring segments in the T2 images taken before the start of treatment and 6 and 12 months after inclusion. The quotient of the value obtained in the affected segment divided by the mean of the healthy segments will be used as a measure of the relative water content, with 1.00 being the normal value. The same ROIs should be used for the measurements obtained at 3 times, before treatment and 6 and 12 months after. The procedure is illustrated in Figure 4 (taken from (Orozco et al., 2011)). The increase

in the quotient approaching the value of 1 is will consider a sign of rehydration. The descriptive analysis of the values of this variable It will be expressed by the mean, standard deviation, 95% confidence interval of the mean.

To find out if there are differences between baseline and at 6 and 12 months, the no test will be used. parametric for paired Wilcoxon data.

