11.5. DIFFICULTIES AND LIMITATIONS OF THE STUDY

As noted above, previous clinical trials show that a considerable improvement (up to 30%) due to the placebo effect. It will therefore be accurate discount this random effect before assessing the effects of MSVs. It is therefore, important evolution in the control group.

Bone marrow donation could be a problem if not enough were found donors. The solution to be used, when possible, by patients undergoing treatment with autologous mesenchymals (in the trial we are conducting in collaboration with CM Teknon) also as allogeneic donors would be the situation ideal, the most economical in terms of required means and the most interesting scientifically.

We have tried to obtain the maximum masking in the test within a design reasonable for this first study. While the "single blind" (patient) design is feasible without serious complications, the "double blind" (researcher) or "triple" (analysis) various logistical and ethical issues, so they have been left for the future. If there are indications of efficacy for allogeneic MSV, it will not be possible to perform direct comparison with autologous MSVs, so if these are obtained results, a new trial should be designed to directly compare the efficacy of both therapeutic alternatives.

REFERENCES:

Adams MA, Dolan P & Hutton WC. (1986). The stages of disc degeneration as revealed by discograms. The Journal of bone and joint surgery 68, 36-41. Adams MA, Freeman BJ, Morrison HP, Nelson IW & Dolan P. (2000). Mechanical initiation of intervertebral disc degeneration. Spine (Phila Pa 1976) 25, 1625-1636. Aggarwal S & Pittenger MF. (2005). Human mesenchymal stem cells modulate allogeneic immune cell responses. Blood 105, 1815-1822.

Bernardo ME, Locatelli F & Fibbe WE. (2009). Mesenchymal stromal cells. Ann N Y Acad Sci 1176, 101-117.

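### Nothing hides the date or order of the images, so the within-arm before-after tests on disc height and the T2 quotient are open to reader expectation even if the reader does not know the arm

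*Combined protocol and SAP*

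**What the plan says.** **Masking.** Section 2.1 promises that "The evaluation of the response to treatment will be blind". The footnote to the Summary, repeated in 4.1, describes the trial as "masked for the patient and evaluators performing the analysis of the results, open to the doctor who applies the cells". Section 11.5 differs: it treats patient blinding as feasible, but of blinding the researcher or the analysis it speaks of "various logistical and ethical issues, so they have been left for the future".

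**When baseline is measured.** Under Visit 0, section 7.2.1 has staff review the imaging and "carry out the measurements that will be taken as a standard of future explorations". Section 4.2 describes the same baseline MRI and films as those "which will be considered the pattern on which the possible determinable changes in the controls at 6 and 12 months" are judged against. Baseline images also serve eligibility: the height-loss criterion in 5.1.1 and annulus integrity in 5.2.2.2.

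**How follow-up is measured.** Section 11.2.1.2 divides the T2 value of the affected disc by the mean of 3-5 healthy neighbouring discs and adds: "The same ROIs should be used for the measurements obtained at 3 times, before treatment and 6 and 12 months after". Neither this section nor 11.2.1.1 says whether the reader sees the dates or the order of the images.

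**How it is tested.** For disc height at baseline against 6 and 12 months, 11.2.1.1 states that "the Wilcoxon nonparametric test for paired data will be used"; 11.2.1.2 names the same test for the quotient. A rise is read as rehydration in both. Section 11.2 also plans a two-group comparison, and 11.3.7 compares the percentage with signs of regeneration between interventions. Section 3.3 lists both imaging measures as primary criteria, although the main objective in 3.1 is feasibility and safety.

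**The concern.** Masking to arm protects a comparison between arms. It does not protect a comparison of before with after, because the reader's expectation attaches to the time point rather than to the treatment. Someone measuring at V0 necessarily knows that the image is a baseline, since no follow-up image exists yet. If that value then stands as the reference for later scans, the follow-up reading is made with its place in the sequence known, unless someone takes steps to conceal it. The plan describes no such steps.

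The direction of expectation is also on record. Section 2.7 reports that the team's autologous pilot found a small but significant rehydration after one year, and the MRI procedure comes from that pilot. An effect expected to be small is one that a modest reading shift can imitate. At stake are the within-arm imaging results, which could be reported as regeneration when nothing has changed.

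**Working it through.** **Inputs from the documents.** 12 patients per arm (11.1); two-sided 5% tests (11.2); paired Wilcoxon test of baseline against follow-up (11.2.1.1 and 11.2.1.2); two-group comparison by t-test or Wilcoxon (11.2). The sample size is fixed by convention, so there is no power figure to reproduce.

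**Assumptions.** No true change. Paired changes are normal with SD 1. A reader who knows the time point shifts every follow-up value by b SDs of the paired change. The documents give neither a reader error nor an SD of change, so b is shown as a range.

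**Step 1: size of the paired test with no shift.** With n = 12 there are 2^12 = 4096 equally likely sign patterns. Of these, 87 give a signed-rank sum of 13 or less, so rejecting at 13 or less in either tail has size 2 × 87 / 4096 = 4.25%. A cut-off of 14 would exceed 5% (2 × 107 / 4096 = 5.2%).

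**Step 2: one within-arm test with a shift, n = 12, by simulation.** Ranges show separate runs.

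| Assumed shift b (SD of paired change) | False-positive rate |
|---|---|
| 0 | 4.2-4.3% |
| 0.2 | 8.3-8.7% |
| 0.25 | 10.8% |
| 0.3 | 13.6-14.0% |
| 0.5 | 31.6-31.7% |

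**Step 3: between-arm test of change, same shift in both arms.** The expected difference is (0 + b) − (0 + b) = 0, so the shift cancels. Simulated rejection with the t-test at 12 per arm is 4.8% to 5.0% for every b from 0 to 1.

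**Step 4: between-arm test if the reader also knows the arm and shifts only the cell arm.** The expected difference is now b. Rejection is 8.7% at b = 0.25 and 21.5% at b = 0.5. The protection in step 3 therefore depends on arm masking, and this is where 11.5 conflicts with the Summary and 4.1.

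**The case against.** Several points against the concern are sound.

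- **The trial is controlled.** The plan compares the groups, and 11.5 says that improvement in the control group must be discounted before the cells are judged. A reader might infer that the whole imaging efficacy result is biased. The documents do not support that: by step 3, a shift common to both arms leaves the between-arm test at about 5% if the reader is masked to arm. This point stands and limits the concern to the within-arm tests.
- **The reader's knowledge is inferred.** The plan does not say who reads the images, whether the same person reads follow-up, or whether baseline is measured again later. It does not exclude a masked re-read. It does, however, name the V0 measurement as the standard, and that reading cannot be blind to time.
- **Reader discretion is limited for the T2 quotient.** Fixed ROIs restrict placement, and dividing by healthy discs in the same patient tends to cancel a general shift. Both may keep b small. Neither applies to disc height in millimetres.
- **The size of b is assumed.** Nothing in the documents shows that 0.2 or 0.5 SD is realistic.
- **Responder percentages.** A reader might go on to calculate how many unchanged discs would count as regenerated. That would require any rise, however small, to make a responder. Section 11.3.7 gives no threshold, and 11.2.1.2 speaks of a rise towards 1, so the documents do not support a figure.

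Finally, efficacy is preliminary here and the main objective is safety. That limits the consequence but does not remove it, because 3.3 calls both imaging measures primary criteria and the imaging sections name only before-after tests.

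**Conclusion.** The concern holds for the within-arm paired tests on disc height and the T2 quotient. As written, a reading known to be baseline feeds those tests, and nothing conceals the date or order of later images. If the reader's shift is 0.2 to 0.5 SD of the paired change and there is no true change, a single test at n = 12 is falsely positive in 8-9% to about 32% of trials, against about 4% with no shift. These figures rest on the assumed shift and on normal changes. They show how sensitive the test is and do not estimate an actual bias. For the quotient the true shift may lie at the low end or below.

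The between-group comparison is not affected by a common shift, on condition that the evaluator is masked to arm. It would be too generous to take that masking as settled, since 11.5 postpones researcher and analysis blinding. It would also be too strong to conclude that there is none, since the Summary and 4.1 both state it. The passages contradict each other and must be reconciled.

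**What to change.** 1. **Reading procedure (11.2.1.1, 11.2.1.2, 7.2.1).** Use V0 readings for eligibility only. For the endpoint, the evaluator masked to arm measures disc height and the T2 quotient at baseline, 6 and 12 months in one session per patient after V5, with dates and visit labels removed, in random order, and with the same ROIs at all three times. This keeps the existing ROI rule. It also separates the endpoint baseline from the reading that selected patients for reduced disc height, which lessens regression to the mean.
2. **Analysis (11.2, 11.2.1.1, 11.2.1.2).** Make the between-arm difference in change the main imaging test and label the within-arm paired tests descriptive.
3. **Masking statements.** Reconcile 11.5 with the Summary and 4.1, so that masking of the imaging evaluator to arm is unambiguous. Items 1 and 2 depend on it.

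**Cost.** Protocol and SAP wording; a second reading of 24 baseline MRIs and 24 baseline films; and removal of labels from 24 patients × 3 time points × 2 modalities = 144 image sets. Imaging endpoint values become available only after V5. No new scans or staff are needed.

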3. OBJECTIVES

In this prospective study that will evaluate the feasibility and safety of local implantation in the nucleus pulposus area of allogeneic MSVs for the treatment of discopathy lumbar degenerative. The working hypothesis contemplated pursues the achievement of long-lasting analgesia and anti-inflammation and regeneration of degenerated IVD in degree enough to be objectifiable by questionnaires and image scans. The approach as a randomized and controlled trial will allow a study preliminary efficacy compared to the control arm,

3.1. Main goal

□ To evaluate the viability and safety of allogeneic MSV, applied by percutaneous injection in the nucleus pulposus area for the treatment of lumbar degenerative disc disease, verifying that each of the the procedures established in the protocol and recording the possible adverse effects related to cell therapy and those that may arise for the duration of the clinical trial, whether or not related to the same.

3.2. Secondary objectives

□ To determine clinical outcomes and image variations

Radiographic and Magnetic Resonance, which denote anti-inflammation, regeneration or, on the contrary, progression of lumbar IVD deterioration, after 12 months after the implementation of MSV in the NP.

□ Compare the efficacy of MSV treatment with that obtained in the arm control.

3.3. Primary Criteria

3.3.1. Radiographic criteria

□ In profile radiography, carried out with the same technical characteristics and hourly (before noon), the height of the space will be measured intervertebral in millimeters, this being the variable that will be compared with measurements that occurred over time (6 and 12 months after implantation of MSV). An increase in height will be understood as rehydration disc associated with an increase in proteoglycans and cellularity of the NP.

3.3.2 Magnetic Resonance Criteria

□ A quantitative assessment of the water content of the affected segments on T2 images (Sakai et al., 2006; Hiyama et al., 2008; Watanabe et al., 2009), following the procedure below illustrated in Figure 4 (see foot for details) (Orozco et al., 2011). The initial values will be compared with those obtained 6 and 12 months after the intervention.

3.4. Secondary criteria

□ Clinical observations of the surgeon

□ Evaluation of lumbar pain and general health status according to the Visual Scale Analog (EVA, see Annex V). The score will be transformed to a scale 0-100% for analysis (Huskisson, 1974)

□ Disability assessment using the Oswestry questionnaire (Davidson & Keating, 2002) (ODI, see Annex VI).

□ Assessment of quality of life using the simplified version of the questionnaire Short Form-36 (Davidson & Keating, 2002). It has been shown that this simplification (SF-12; see Annex VII) has a statistical value that approximates much the complete test (Gandek et al., 1998).

4. TYPE OF CLINICAL TRIAL AND DESIGN OF THE SAME 4.1 Type of CT

Phase I-II clinical trial, single-center, prospective, randomized, blinded **, controlled for the treatment of lumbar degenerative disc disease with intact fibrous ring proven by MRI, with two arms: a control arm with placebo treatment (injection of mepivacaine at 1%) and another experimental arm treated with allogeneic MSV. This is the third application of a PEI consisting of Ex vivo expanded bone marrow mesenchymal cells (PEI No. 10-1349). In both cases, the product will be administered in a volume of 2 ml per injection in the nucleus pulposus area.

** Double blind, masked for the patient and evaluators performing the analysis of the results, open to the doctor who applies the cells.

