Disc degeneration has different clinical translations. May lead to herniation disc material and, depending on the location, generate symptoms ranging from isolated low back pain and / or associated with radiculopathy, myelopathy or claudication neurogenic disease associated with canal stenosis. According to the degree of invasion of the structures next we speak of protrusion or hernia. On many occasions, however, there is pain lumbar without herniation and with integrity of the fibrous ring. It is in these cases when proposes the treatment described in this RC.

The first step of treatment includes physical measures for stabilization of the lumbar spine. Both by external means (girdles or corsets), and, mainly, by toning the abdominal and spinal muscles through exercises isometric that do not require mobilization of the lumbar spine. As a complement of these measures the weight will be controlled to an adequate level and measures will be implemented of postural hygiene: by using ergonomic chairs and furniture, avoiding flex the spine forward and keep the weights close to the body. The use of both non-steroidal anti-inflammatory drugs such as corticosteroids, analgesics and the Muscle relaxants may be helpful in periods of exacerbation of pain. The application of currents, massages, tractions and heat in rehabilitation and acupuncture can improve symptoms temporarily. The next step includes periarticular infiltrations of local anesthetic and corticosteroids, which can serve both as a diagnosis of the origin of the pain and treatment of the acute phase. The final step is surgery, in which the lumbar spine is stabilized by fixing the affected vertebrae. Surgical treatment is necessary when the condition clinical is intense and refractory to drug and rehabilitation treatments. The discectomy associated or not with vertebral segment arthrodesis is the "gold standard" and its efficacy is beyond question (Errico et al., 2004; Kwon et al., 2006). Fixing is done with the patient's own bone graft and is facilitated with metal implants. On discs degenerates expressed as a protrusion

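### The control arm cannot separate the cells from the rest of the intradiscal MSV procedure, so the placebo label and the subtraction in Section 11.5 claim more than the design can show

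*Combined protocol and SAP*

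**What the plan says.** **Label.** Section 4.1 describes "a control arm with placebo treatment (injection of mepivacaine at 1"%). The visit programme in Section 7.2.1 repeats it for day 1: "Placebo injection or allogeneic MSV, depending on the clinical trial arm".

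**Content and site.** Section 1 says: "The control arm will infiltrate the area of the paravertebral musculature close to the injury with saline solution containing mepivacaine at 1"%. Section 4.2 gives the mixture as "saline serum containing 1% mepivacaine (1 ml of 2% mepivacaine + 1 ml of saline) in identical volume". Sections 2.1, 2.6 and 6.1 and Annex I also place the injection in paravertebral muscle. Section 6.1 adds usual treatment (physiotherapy, postural hygiene, drugs) to the control. Sections 1, 2.1, 2.6, 4.2 and 6.1 say that the control undergoes the same maneuvers as the experimental arm. Shortly after the placebo wording, however, Section 4.1 states that both arms receive their 2 ml in the nucleus pulposus area.

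**Experimental arm.** Sections 1 and 6.1.3 describe puncture of the disc and injection of 2 ml of cells in Ringer-lactate with 0.5% albumin and 5 mM glucose.

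**Use of the control.** The secondary objective in Section 3.2 is "Compare the efficacy of MSV treatment with that obtained in the arm control". Section 11.5 expects "considerable improvement (up to 30%) due to the placebo effect" and says the analysis must "discount this random effect before assessing the effects of MSVs". Sections 3.3.1 and 11.2.1.1 read a gain in disc height as rehydration linked to more proteoglycans and more cells in the nucleus.

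**The concern.** Subtracting a control response leaves the effect of the cells only if the two arms are alike in everything else. Section 11.5 treats the control as if it had that property, and the placebo label tells readers that it does. The described components do not bear this out.

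Two conclusions are at stake. The first is efficacy: a difference in VAS, Oswestry, SF-12, disc height or T2 ratio could be reported as an effect of the cells when puncture, injected volume or carrier may have contributed. The second is safety: Sections 2.6.3 and 6.1.5 liken the complications to those of discography and name a pain flare of 1 to 2 weeks as the most common complaint. The day-8 safety visit falls inside that window. If only one arm has its disc punctured, an excess of such events in that arm cannot be assigned to the cells.

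Section 11.5 discusses donor supply, masking and the missing comparison with autologous cells, but not this limitation.

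**Working it through.** The plan gives no figure to reproduce: Sections 5.4 and 11.1 fix 12 patients per arm without an effect size, standard deviation or power. The check is therefore a comparison of components.

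| Component | MSV arm | Control: Sections 1, 2.1, 2.6, 4.2, 6.1, Annex I | Control: Section 4.1 sentence taken literally |
|---|---|---|---|
| Cells | 25 ± 5 million per disc | none | none |
| Fluid | 2 ml Ringer-lactate, albumin, glucose | 2 ml saline with 1% mepivacaine | 2 ml saline with 1% mepivacaine |
| Disc puncture | yes | no | yes |
| Volume into the disc | 2 ml | 0 ml | 2 ml |
| Site of study mepivacaine | not given | paravertebral muscle | nucleus pulposus area |

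**Step 1, main reading.** MSV minus control = cells + carrier + disc puncture + 2 ml in the disc − mepivacaine in saline in muscle. Only the first term is the cells.

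**Step 2, literal reading of Section 4.1.** Puncture and volume cancel. What remains is cells + carrier − mepivacaine in saline in the disc. This still does not reduce to the cells.

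**Step 3, which reading the text favours.** Six places describe muscle. The patient replacement rule (end of Section 5.6, listed as 5.7 in the index) requires infiltration of the intervertebral space only for MSV patients. The conflict still stands in the text and must be reconciled. The conclusion does not depend on how.

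**Step 4, whether the documents show the other components to be neutral.** The reassurance offered on puncture is a discography follow-up with no progressive degeneration on radiographs (Sections 2.6.3, 6.1.5). It does not address pain, disability or T2 signal. Nothing is said about the carrier alone.

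**Step 5, direction.** Any analgesia from the control injection would work against MSV on pain. Puncture, volume and carrier could act either way. Section 6.1.3 also puts local anaesthetic into the muscle in the cell procedure, so that exposure is partly shared. The net sign is unknown.

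**Illustration, not an estimate.** Assume the cells do nothing and the other components differ by d standard deviations in either direction. With 12 per arm, a two-sided 5% t-test has 2 × 12 − 2 = 22 degrees of freedom and noncentrality d × √(12/2). The chance of a significant difference is 5.0% at d = 0, 7.6% at 0.2, 21.6% at 0.5 and 46.6% at 0.8. Every value of d is an assumption; the documents supply none.

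**The case against.** The strongest reply has four parts.

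- **Section 3.2 asks only for an arm-versus-arm comparison.** This stands. It does not mention placebo or cells alone, and the randomised trial answers it. A reader might infer that the design fails its stated secondary objective; the text does not support that. The over-attribution sits in Section 11.5 and in the label in Sections 4.1 and 7.2.1.
- **The carrier belongs to the product.** Largely fair: Sections 2.6.1 and 6.1 define MSV as cells in that medium. It supports attribution to the product, not to the cells. It does not cover puncture and volume on the main reading.
- **The control is not shown to be an active treatment.** This also stands. Section 2.4 mentions "infiltrations of local anesthetic and corticosteroids, which can serve both as a diagnosis of the origin of the pain and treatment", but the sentence goes on to limit this to the acute phase, and it concerns infiltrations that include corticosteroids. Trial patients have pain persisting after conservative treatment, with more than 6 months of evolution, and scores are first compared at 3 months. A lasting effect of one plain anaesthetic injection is not supported.
- **The aim is feasibility and safety.** Section 3 calls the efficacy study preliminary, causality of events is graded (Section 8.2), and the named safety variables are related serious events (Section 11.2.1). This limits the consequence but does not remove it: Section 7.1.1 makes the clinical scores and MRI the main evaluation variable.

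**Conclusion.** The point holds as one of attribution. On either reading of the injection site no arm receives the carrier without cells, and on the main reading the arms also differ in puncture and intradiscal volume. A between-arm difference may be attributed to the intradiscal MSV procedure as a whole, not to the cells alone.

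No size can be given. A reader might multiply the 30% in Section 11.5 by the share of placebo response that a muscle injection misses and call the result bias in favour of MSV. The documents do not support this: the 30% is an upper bound with no stated scale, no share is given, and the components can act in opposite directions.

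Two other inferences go too far. The absence of disc puncture in controls is not settled while Section 4.1 says otherwise. Usual treatment is not an established arm difference either: Section 6.1 names it only for controls, but Section 7.2.1 prescribes the standard regimen to candidates before inclusion. Randomisation and the comparison of whole packages remain sound.

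**What to change.** Keep both arms and correct what may be concluded.

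1. Reconcile the control injection site in Section 4.1 with Sections 1, 2.1, 2.6, 4.2 and 6.1 and Annex I. Reconcile the same-maneuvers wording wherever it appears.
2. In Sections 4.1 and 7.2.1, replace the placebo label with a description of the actual control: mepivacaine injection at the reconciled site plus usual treatment.
3. In Sections 3.2 and 11.2, state that the between-arm contrast is the whole intradiscal MSV procedure (puncture, carrier and cells) versus that control.
4. In Section 11.5, replace the subtraction sentence with a statement that the control does not isolate the cells from puncture, volume and carrier, and that a difference will be attributed to the MSV procedure as a whole. Apply the same limit to procedure-related adverse events and to the reading of disc height as nucleus cellularity in Sections 3.3.1 and 11.2.1.1.

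The cost is a written amendment under Section 9.2 touching these sections. Items 2 to 4 change no treatment, visit or sample size, and item 1 only asks that the text agree with itself. The downside is a narrower efficacy claim.
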